7.3.4. Phone Contact during the placebo run-in period (approximately Week -1)

Contact patient by phone approximately one week after the Week -2 visit:

- Assess for potential adverse events by asking the patients to respond to a non-leading question such as “how have you been feeling?” and “has anything changed since your last visit?”
- Confirm sponsor CGM sensor is still attached, with no adherence issues. For sensor issues, subjects may need to return to the site for replacement.
- Query circumstances around any extreme episodes of hypoglycemia or hyperglycemia and record relevant information (e.g. glucometer readings or contributing factors)

7.3.5. Week 0/Day 1

On Week 0/Day 1 patients will return to the site after an overnight fast (except water or glucose tablets if needed for low blood glucose). If the patient is not fasted or the subject did not return the Week -2 study drug, the visit should be rescheduled.

Visit should be scheduled no earlier than 13 days after the prior Week -2 visit to allow for at least 13 days of collection for the sponsor provided CGM.

At this visit, the following procedures will be completed **prior** to administration of study medication:

- Confirm patient is fasting. If not fasted, the visit should be rescheduled;
- Conduct inquiry about baseline symptoms by asking the patients to respond to a non-leading question such as “how have you been feeling?” and “has anything changed since your last visit?” and record any changes in medical history;
- Collect prior periods study drug and perform compliance check prior to dispensing and dosing at the visit;
- Update concomitant medications;
 - Review Inclusion/Exclusion Criteria to confirm eligibility;

Note: if a patient does not qualify for the trial after being enrolled, but prior to randomization, he or she will be considered a run-in failure.
- Conduct limited physical exam [refer to Section 8.3];
- Obtain body weight [refer to Section 8.2];
- Obtain standard supine 12-lead electrocardiogram (ECG) prior to blood sampling (Triplicate) [refer to Section 8.4];
- Obtain sitting vitals (blood pressure and pulse rate) prior to blood sampling (Triplicate) [refer to Section 8.5];
- Collect clinical laboratory specimens per lab kit [refer to Section 8.7 and Table 1 (Part 1) and Appendix 2 (Part 2)];
- Collect pharmacokinetic samples prior to dosing;
- Collect retention samples if applicable (optional);
- Obtain urine void (pregnancy test (if applicable) and urinalysis) [refer to Section 8.7.2 and Table 2 for list of tests];
- Collect CGM device and data;
- Collect basal and bolus insulin dosing information;
- Provide any insulin dosing adjustment information based on the glycemic values using the guidance in Section 8.11;
- Randomize the patient to one of the double-blind treatment regimens;

Note: IWRS will assign a randomization ID to the patient once the patient is randomized, the patient can no longer be considered Run-In failure.
- Dispense study drug according to the IWRS [Refer to Sections 6.1.2 and 6.4.2];
- Dose with study drug; document date and time of administration;
- Have patient eat their morning meal (either provided by the site or brought to the site by the patient) to establish a routine of dosing the study drug with their morning meal;
- Adverse-event reporting for double-blind treatment period will begin immediately following the administration of the first dose of double-blind study medication.

Prior to discharging the patient from the visit:

- Provide instructions for at home dosing for the next period [Refer to Section 6.5.2];
- Instruct patients regarding identification/ management of hypoglycemia, hyperglycemia and diabetic ketoacidosis;
- Provide the patient with glucometer and other supplies (if needed);
- Remind patient to return to the study site for the next study visit in approximately two weeks with study drug and personal CGM (if applicable) or glucometer for a safety visit;

7.3.6. Phone Contact during the first week of dosing (approximately Week 1)

Contact patient by phone approximately one week after the Week 0/Day 1 visit

- Assess for potential adverse events by asking the patients to respond to a non-leading question such as “how have you been feeling?” and “has anything changed since your last visit?”
- Query circumstances around any extreme episodes of hypoglycemia or hyperglycemia and record relevant information (e.g. glucometer readings or contributing factors)
- Record any insulin adjustments in the EDC [Refer to Section 8.11]

7.3.7. Week 2 and Week 6

On Week 2 and Week 6, patients will return to the site after an overnight fast (except water).

At this visit, the following procedures will be completed **prior** to administration of study medication:

- Conduct inquiry about potential symptoms by asking the patients to respond to a non-leading question such as “how have you been feeling?” and “has anything changed since your last visit?”
- Update concomitant medications;
- Obtain body weight [refer to Section 8.2];
- Obtain standard supine 12-lead electrocardiogram (ECG) prior to blood sampling (single readings) [refer to Section 8.4];
- Obtain sitting vitals (blood pressure and pulse rate) prior to blood sampling (single readings) [refer to Section 8.5];
- Collect clinical laboratory specimens per lab kit [refer to Section 8.7 and Table 1 (Part 2) and Appendix 2 (Part 2)];
- Collect pharmacokinetic sample prior to dosing (Week 6 only);
- Collect retention samples, if applicable (optional) (Week 6 only);
- Obtain urine void (pregnancy test (if applicable) and urinalysis) [refer to Section 8.7.2 and Table 2 for list of tests];
- Collect basal and bolus insulin dosing;
- Provide any insulin dosing adjustment information based on the glycemic values using the guidance in Section 8.11;
- Collect prior periods study drug and perform compliance check;
- Dispense study drug according to the IWRS along with instructions for at home dosing for the next period [Refer to Section 6.4.2 and 6.5.2]

Following completion of the above procedures:

- Remind patients regarding identification/ management of hypoglycemia and hyperglycemia and diabetic ketoacidosis;
- Provide the patient with glucometer and supplies (if needed);
- Remind patient to return to the study site for the next study visit with study drug and personal CGM (if applicable) or glucometer;

7.3.8. Phone Contact during double-blind dosing period (approximately Week 4 and 8)

Contact patient by phone at approximately Week 4 and Week 8

- Assess for potential adverse events by asking the patients to respond to a non-leading question such as “how have you been feeling?” and “has anything changed since your last visit?”
- Review glucose and insulin data with the patient
 - Provide any insulin dosing adjustments based on the glycemic values of last 2-3 days using the guidance in Section 8.11;
- Query circumstances around any extreme episodes of hypoglycemia or hyperglycemia and record relevant information (e.g. glucometer readings or contributing factors)
- Record any insulin adjustments in the EDC [Refer to Section 8.11]

7.3.9. Week 10

On Week 10, patients are NOT required to be fasted for this visit.

- Conduct inquiry about potential symptoms by asking the patients to respond to a non-leading question such as “how have you been feeling?” and “has anything changed since your last visit?” Update medications;
- Collect urine for pregnancy test if applicable;
- Collect prior periods study drug and perform compliance check prior to dispensing and dosing at the visit;
- Dispense study drug according to the IWRS along with instructions for at home dosing for the next period [Refer to Section 6.4.2 and 6.1.2]
- Apply sponsor CGM and review requirements [See Section 4.2];
- Collect basal and bolus insulin dosing information;

Prior to discharging the patient from the visit:

- Remind patients regarding identification/ management of hypoglycemia, hyperglycemia and diabetic ketoacidosis;
- Provide the patient with glucometer and other supplies (if needed);
- Remind patient to return to the study site for the next study visit in approximately two weeks with study drug and sponsor CGM and personal CGM (if applicable) or glucometer;

7.3.10. Week 12

On Week 12, patients will return to the site after an overnight fast (except water). Visit should be scheduled no earlier than 13 days following the Week 10 visit to allow for at least 13 days of collection for the sponsor provided CGM.

At this visit, the following procedures will be completed **prior** to administration of study medication:

- Conduct inquiry about potential symptoms by asking the patients to respond to a non-leading question such as “how have you been feeling?” and “has anything changed since your last visit?”
- Update medications;
- Provide DTSQs and DTSQc for patient to complete [refer to Section 8.12];
- Ask Quality of Life Question and enter answer in EDC [refer to Section 8.13];
- Conduct limited physical exam [refer to Section 8.3]
- Obtain body weight [refer to Section 8.2];
- Obtain standard supine 12-lead electrocardiogram (ECG) prior to blood sampling (single reading) [refer to Section 8.4];
- Obtain sitting vitals (blood pressure and pulse rate) prior to blood sampling (single reading) [refer to Section 8.5];
- Collect clinical laboratory specimens per lab kit [refer to Section 8.7 and Table 1 (Part 2) and Appendix 2 (Part 2)];
- Collect pharmacokinetic samples;
- Collect retention samples, if applicable (optional)
- Obtain urine void (pregnancy test (if applicable) and urinalysis) [refer to Section 8.7.2 and Table 2 for list of tests];
- Collect CGM device and data;
- Collect basal and bolus insulin dosing information;
- Collect prior periods study drug and perform compliance check;

Following completion of the above procedures:

- Remind patients regarding identification/ management of hypoglycemia and hyperglycemia and diabetic ketoacidosis;

7.3.11. Follow-up (F/U); 7-10 days following the last dose

Patients will return to the study site after an overnight fast (except water) for a follow-up visit at 7-10 days after the last dose. If the last dose occurs at the Early Termination visit or within 10 days of the ET, a Follow-up visit will occur 7-10 days after the Early Termination visit. If an Early Termination visit is conducted the Follow-up visit will occur 7-10 days after the Early Termination visit.

The following procedures should occur at the visit:

- Conduct inquiry about baseline symptoms by asking the patients to respond to a non-leading question such as “how have you been feeling?” and “has anything changed since your last visit?”
- Update medications;
- Obtain body weight [refer to Section 8.2];
- Obtain standard supine 12-lead electrocardiogram (ECG) prior to blood sampling [refer to Section 8.4];
- Obtain sitting vitals (blood pressure and pulse rate) prior to blood sampling (single readings) [refer to Section 8.5];
- Collect clinical laboratory specimens according to lab manual/kit [refer to Section 8.7, Table 1 (Part 2) and Appendix 2 (Part 2)];
- Obtain urine void (pregnancy test (women only) and urinalysis) [refer to Section 8.7.2 and Table 2 for list of tests];

Completion of the follow-up visit marks the end of the patients' participation in the study.

- The Investigator may provide guidance to the patient regarding management of their T1DM and related conditions

CGM and study related supplies for home glucose, insulin dosing and DKA monitoring (if supplied by the site) can be returned to the patients for their use, if permitted by local country regulations.

7.3.1. Early Termination (ET) Procedures [Same as Week 12 (except treatment questionnaire and QOL question)]

See Section 7.3 as to when to conduct an ET visit.

- Conduct inquiry about potential symptoms by asking the patients to respond to a non-leading question such as “how have you been feeling?” and “has anything changed since your last visit?”
- Update medications;
- Conduct limited physical exam [refer to Section 8.3];
- Obtain body weight [refer to Section 8.2];
- Obtain standard supine 12-lead electrocardiogram (ECG) prior to blood sampling (single readings) [refer to Section 8.4];
- Obtain sitting vitals (blood pressure and pulse rate) prior to blood sampling (single readings) [refer to Section 8.5];
- Collect clinical laboratory specimens per lab kit [refer to Section 8.7 and Table 1 (Part 2)];
- Collect pharmacokinetic samples;
- Collect retention samples, if applicable (optional);
- Collect prior periods study drug and perform compliance check;

- Obtain urine void (pregnancy test (if applicable) and urinalysis) [refer to Section 8.7.2 and Table 2 for list of tests];
- Collect insulin data, insulin pump settings (patients using pumps) or basal insulin dose (for patients using MDI) in the EDC as directed in the Study Procedures Manual;

Following completion of the above procedures:

- Remind patients regarding identification/ management of hypoglycemia and hyperglycemia and diabetic ketoacidosis;

7.3.2. Patient Withdrawal

Patients may withdraw from the study at any time at their own request, or they may be withdrawn at any time at the discretion of the Investigator or Sponsor for safety, behavioral, or administrative reasons.

If a patient does not return for a scheduled visit, every effort should be made to contact the patient. Every effort should be made to document patient outcome. The Investigator should inquire about the reason for withdrawal. The patient must return all unused study medication to the site and should return to the site for one or two visits, as described below.

Any AEs should be followed based on the following criteria:

Follow-up of any ongoing AE (including any clinically significant laboratory abnormality) should be conducted as follows:

- If the Investigator determines the AE is *not related* to the study product or study procedures, the AE will be followed until resolution, or 60 days from end of study participation.
- All AEs with a relationship other than *not related* will be followed until resolution, or until the patient is lost to follow-up.

At the discretion of the Investigator or designated licensed physician and Medical Monitor, the length of AE follow-up may be attenuated, with written rationale by the Investigator or designated licensed physician.

Upon termination, all patients who continue to consent will have a Follow-up Visit approximately 7-10 days after the last dose. Procedures leading up to the Follow-up Visit will depend on the patient's recent dosing and how long the patient has been on treatment. The following table summarizes what exit visits should be conducted upon termination assuming patient still consents:

Patient dosing/treatment status at termination:	Other applicable conditions:	Exit Visits to be conducted:
Patient has not received 4 weeks of treatment	None	Do not complete Early Termination visit. Conduct Follow-up Visit approximately 7-10 days after last dose.
Patient has not dosed within 10 days of initiating termination procedures	None	Do not complete Early Termination visit. Only conduct Follow-up Visit
Patient has dosed within 10 days of initiating termination procedures	Patient has reach 12 weeks of treatment (i.e., reached the Week 12 visit window of 12 weeks \pm 3 days). Patient will be considered to have completed treatment but not complete the study.	Do not complete Early Termination visit. Conduct Week 12 visit then a Follow-up Visit approximately 7-10 days later
	Patient has completed at least the Week 6 Visit but has not reached 12 weeks of treatment	Conduct Early Termination Visit then a Follow-up Visit approximately 7-10 days later

If the patient withdraws consent for further assessments, no further evaluations will be performed, and no additional data will be collected. The Sponsor may retain and continue to use any data collected before such withdrawal of consent.

Patients who terminate early may result in additional enrollment of patients to accommodate dropouts, at the Sponsor's discretion.

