	Patient has completed at least the Week 4 Visit but has not reached 12 weeks of treatment	Conduct Early Termination Visit then a Follow-up Visit approximately 7-10 days later
--	---	--

If the patient withdraws consent for further assessments, no further evaluations will be performed, and no additional data will be collected. The Sponsor may retain and continue to use any data collected before such withdrawal of consent.

Patients who terminate early may result in additional enrollment of patients to accommodate dropouts, at the Sponsor's discretion.

7.3. PART 2

A complete list of all trial procedures can be found in the [SCHEDULE OF ACTIVITIES \(Part 2\)](#).

Each outpatient site visit should occur as early in the morning hours as possible. Beginning with the Week0/Day1 visit and continuing through follow-up visits (except the Week 10 visit), patients will be instructed to arrive at the site following an overnight fast, before their morning meal, before taking mealtime insulin and before taking their study medications for that day. An overnight fast must be observed prior to safety and efficacy laboratory sample collection. Additionally, ECG and vital sign assessments should precede the blood collection.

Patients are expected to bring all remaining study drug at Week 0/Day 1 and Week 26, 10 and 12 and ET (if applicable).

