PART 2 Sample Type	Maximum proposed sample Volume (mL)	Number of Sampling Times				Total Volume ^a (mL)
		Screening	Double- Blind Treatment	Follow-Up Visit (F/U)	Total Number of Samples	
Clinical Laboratory Tests (hematology, chemistry and glycemia biomarkers ^b)	10.5	1	4	1	6	63
HbA1c	4	1	4	1	6	24
PK (TTP399)	4	---	3	---	3	12
Fasting c-peptide	2	-	3	-	3	6
Fasting Glucagon ^c	2		3		3	6
Retention sample (optional)	4	---	3	---	3	12
TOTAL						123

a. Additional blood samples/volume may be taken for repeats and safety testing.
b. In addition to HbA1c and glucagon, glycemic biomarkers to be collected in Part 2 include fructosamine, 1,5 anhydroglucitol, and c-peptide
c. In addition to glucagon additional exploratory analytes (non-genomic) that may be analyzed in the glucagon sample include amylin, ghrelin, GLP-1, GIP, IL-6, Leptin, MCP-1, PP, PYY and TNF- α

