- D. The population-level summary for the variable that provides, as required, a basis for a comparison between treatment conditions:

For this study, the population-level summary for the variable is the least-squares mean (LSM) of the treatment difference in mean change from baseline in HbA1c.

4 Populations of Analysis

In accordance with guidance from the International Conference on Harmonisation of Technical Requirements for Registration of Pharmaceuticals for Human Use (ICH) *Statistical Principles for Clinical Trials E9* (1998), the following population of analysis will be used for all statistical analysis:

- The full analysis set (FAS) includes all randomized patients who receive at least one dose of randomized study medication with at least one valid value post-treatment value. The FAS is used for all efficacy analyses.
- The per-protocol set (PPS) includes all FAS patients who do not have significant protocol violations, where a significant protocol violation is one that has the potential to affect analysis conclusions. Final determinations of significant protocol violations will be made at the final blinded data review meeting in accordance with guidance from ICH E9 (Statistical Principles).
- The safety analysis set (SAF) includes all patients who received at least one dose of study medication. The SAF is used for all safety analyses.

In accordance with ICH E9, patients lacking any valid, on-treatment assessment of HbA1c will be excluded from the FAS.

It is noted that the evaluations, reviews, and decisions planned to be made at blind data review meetings are consistent with regulatory guidance as depicted and recommended in ICH E9.

Solely to understand the influence of dropouts on study conclusions, the FAS will be partitioned into completers and dropouts.

Efficacy analysis will be done as randomized. Safety analysis will be done as treated.

PK analyses will be performed using the PK population, comprising those study participants who have received TTP399 and have sufficient PK data for analysis.

5 Specification of the Estimand

In accordance with guidance from the International Conference on Harmonisation of Technical Requirements for Registration of Pharmaceuticals for Human Use (ICH) ICH E9 (R1) Addendum On Estimands and Sensitivity Analysis In Clinical Trials to the Guideline to Statistical Principles for Clinical Trials (2018), the characterization of the estimand includes the following attributes:

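### Part 2 exit-visit table has no row for patients who stop between 4 weeks of treatment and the Week 6 visit; under Appendix 2 they have no post-dose HbA1c and leave the SAP's full analysis set

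*Protocol*

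**What the plan says.** The Part 2 table in Protocol Section 7.3.2 (Patient Withdrawal) sorts patients who stop into four cases:

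1. "Patient has not received 4 weeks of treatment": no ET visit, Follow-up Visit only.
2. "Patient has not dosed within 10 days of initiating termination procedures": no ET visit, Follow-up Visit only.
3. Dosed within 10 days and already in the Week 12 window: Week 12 visit, then Follow-up Visit.
4. Dosed within 10 days and "Patient has completed at least the Week 6 Visit but has not reached 12 weeks of treatment": ET visit, then Follow-up Visit.

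The text before the table adds a general rule: "Upon termination, all patients who continue to consent will have a Follow-up Visit approximately 7-10 days after the last dose". The Part 2 ET section gives no criterion of its own and refers the reader back to Section 7.3.

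The Part 1 table (Section 7.2.9) has the same layout, but its ET row reads "Patient has completed at least the Week 4 Visit but has not reached 12 weeks of treatment".

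Two places give the Part 2 HbA1c schedule. Appendix 2 marks HbA1c at Screening, Week 0, Week 6 and Week 12/ET, with none at Week 2 or Follow-up. The HbA1c row of Table 1 (Section 8.7.1) reads "HbA1c 4 1 4 1 6 24". In column order that is 4 mL per sample, 1 at Screening, 4 in the double-blind period, 1 at Follow-up, 6 in all, 24 mL.

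SAP Section 4 defines the FAS as "all randomized patients who receive at least one dose of randomized study medication with at least one valid value post-treatment value" and then removes anyone without a valid on-treatment HbA1c. Section 7.6.1 repeats the exclusion. Protocol Section 10.4 asks only for a dose and a baseline, but Section 10 lets the SAP override the protocol on analysis.

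**The concern.** Row 1 ends at 4 weeks of treatment and the ET row begins at the Week 6 visit. Nothing covers the interval between them for a patient who is still dosing or has just stopped. Up to 20 sites would have to settle such cases themselves, and the only instruction they can point to is the general Follow-up rule.

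The primary endpoint is at stake. If no on-treatment HbA1c is drawn before the patient leaves, the SAP does not treat the patient as having missing data. It removes the patient from the FAS. The multiple imputation and non-responder imputation in SAP Section 7.5 then never apply, and the patient drops out of the responder comparison instead of counting as a non-responder. This sits badly with the intent-to-treat principle stated in SAP Section 7.6.1, because the exclusion depends on something that happens after randomization.

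**Working it through.** **Step 1. Does any patient fit no row?** Take a consenting patient with at least 4 weeks of treatment, a dose within 10 days, and no completed Week 6 visit.

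- Row 1 fails: 4 weeks have been received.
- Row 2 fails: there is a recent dose.
- Row 3 fails: Week 12 has not been reached.
- Row 4 fails: the Week 6 visit is not done.

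No row applies. The general rule gives a Follow-up Visit and nothing assigns an ET visit.

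**Step 2. How wide is the gap?** It runs from Day 28 to the Week 6 visit at Day 42 ± 3. That is 42 − 28 = 14 days nominally, and between 39 − 28 = 11 and 45 − 28 = 17 days across the window.

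**Step 3. Is there a post-dose HbA1c?** Under Appendix 2 there is none, because the first post-dose draws are at Week 6 and Week 12/ET. Table 1 disagrees. Its Part 2 volumes add up as follows:

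- laboratory tests: 10.5 × 6 = 63
- HbA1c: 4 × 6 = 24
- PK: 4 × 3 = 12
- C-peptide: 2 × 3 = 6
- glucagon: 2 × 3 = 6
- retention: 4 × 3 = 12

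The sum is 123 mL, which is the printed total. With the 4 HbA1c draws of Appendix 2, HbA1c takes 4 × 4 = 16 mL and the sum is 115 mL. The two schedules therefore conflict. Four double-blind draws match Weeks 0, 2, 6 and 12, so Table 1 implies a Week 2 value.

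**Step 4. Can the Follow-up Visit supply the value?** No. Appendix 2 has no HbA1c there. Even if one were drawn, as Table 1 suggests, SAP Section 7.1 keeps Follow-up data out of the efficacy analysis.

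**Step 5. How many patients?** The documents state no dropout rate. Assume a total rate d, spread evenly over 84 days, with 90 randomized. The expected number in the gap is 90 × d × 14/84, and the number stopping at any time before Week 6 is 90 × d × 42/84.

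| d | in the gap | before Week 6 in all |
|---|---|---|
| 5% | 0.75 | 2.25 |
| 10% | 1.5 | 4.5 |
| 20% | 3.0 | 9.0 |

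With 11 or 17 days in place of 14, the 10% figure becomes 1.2 or 1.8 and the 20% figure 2.4 or 3.6. Each count includes everyone who stops in the interval. Some would fall under row 2 or would have withdrawn consent, so the number missed for lack of a row is smaller.

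**Step 6. Does power suffer?** First, the plan's own figure (difference 0.7, SD 1, two-sided alpha 0.049, 80% power). The normal approximation is n = 2 × (1.969 + 0.842)² × 1² / 0.7² = 32.2, or 33 per group. The noncentral t calculation gives power 0.797 at 33 and 0.809 at 34, which reproduces the stated 34. With 90 analyzed, power is 0.906; with 88 it is 0.899; with 86, 0.892; with 81, 0.873. Losing the gap patients costs about a percentage point.

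**The case against.** The best counter-argument is that the loss of HbA1c is not certain. Table 1 implies a Week 2 draw, the Part 2 Schedule of Activities marks glycemic markers at Week 2, and Section 7.3.7 refers sites to both Table 1 and Appendix 2 for that visit. If Week 2 is drawn, gap patients have a post-dose value and stay in the FAS. This stands, and it makes the consequence conditional. It does not remove the point: the Schedule's footnote sends the reader to Appendix 2 for Part 2, where Week 2 is blank. A Week 2 value would also not show HbA1c at the time of stopping.

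A reader might infer that tolerability data on early stoppers are lost. The documents do not support that. The Follow-up Visit includes weight, ECG, vital signs and laboratory samples, adverse events are followed up, and the safety set keeps every dosed patient. The main summary of treatment-emergent events (SAP Section 7.7.1) runs through follow-up. SAP Section 7.1 does limit the use of Follow-up data, but for all patients, not because of this gap.

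A reader might also infer that closing the gap restores an intent-to-treat set. It does not. At 10% dropout, 4.5 − 1.5 = 3 of the 4.5 patients who stop before Week 6 do so before 4 weeks. Row 1 plainly gives them no ET visit, and the SAP's FAS definition then excludes them.

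Nor should Part 1 be read as an exact model. Its first row counts weeks of treatment and its ET row counts a completed visit, so the two meet only to within the visit window.

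**Conclusion.** The missing row is a real inconsistency in the Part 2 table. It reads as a drafting residue, not a choice: Amendment 5 removed the Part 2 Week 4 visit and added Week 6, and the 4-week limit in row 1 appears to have been left behind.

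Exclusion from the FAS follows if Appendix 2 is the operative HbA1c schedule, and does not follow if the Week 2 draw implied by Table 1 is taken. On the assumed 5% to 20% dropout, evenly spread, about 1 to 3 of 90 patients at the nominal visit day are involved, and this leans high because it counts everyone who stops in the interval. The effect is lost HbA1c outcome data and a small post-randomization exclusion. It is a minor point, worth correcting because it touches the primary endpoint and costs little.

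**What to change.** - In the Part 2 table, reconcile the first row and the ET row so that each patient who stops falls in exactly one case. Using the same unit in both rows (weeks of treatment or visit completed) would avoid a new gap at the boundary.
- Keep an on-treatment HbA1c draw for patients who stop between 4 weeks and the Week 6 visit. The existing ET panel in Appendix 2 already contains it.
- Align Table 1 with Appendix 2 on the Part 2 HbA1c schedule, at Week 2 and at Follow-up, and correct the blood volume if the count changes (123 mL with six draws, 115 mL with four).
- Separately, reconcile the FAS definitions in Protocol Section 10.4 and SAP Section 4. The changes above leave patients who stop before 4 weeks outside the SAP's FAS if Appendix 2 is followed.

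The first three changes need a protocol clarification and perhaps one to three exit visits of a kind the protocol already describes. The last is a wording change in the SAP or protocol and needs no new data collection.
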